### 5.6.5. Vital signs, physical findings and other observations related to safety

The baseline is defined as the last measure before the first trial product administration. Vital signs will be analyzed quantitatively and qualitatively by trial product group. Qualitative analyses of Systolic/Diastolic Blood Pressure (mmHg) and Pulse Rate (beats/min) will be done via comparison of vital signs data to their normal ranges. Normal ranges for the shift tables are [90; 160]

CONFIDENTIAL	
STATISTICAL ANALYSIS PLAN N° GDX-44-006
 
VERSION N° 2.0      DATED: 24JUL2018
 
██████████
	
██████████
 
Page 37 / 57

--------------	--	---

mmHg for SBP, [45; 90] mmHg for DBP and [45; 80] for pulse rate. Quantitative analyses of the same parameters will be done by tabulating raw data and change from baseline.

Listings of weight and vital signs will be provided in CSR appendix 16.2.9, including all other parameters recorded in the database [BMI (kg/m^2), Systolic/Diastolic Blood Pressure (mmHg), Pulse Rate (beats/min)] and flag for clinically significant.

Holter ECG parameters will only be listed.

The baseline is defined as the mean of the ECGs triplicates measured before each IMP/AMP administration.

12-lead safety ECG will be analyzed quantitatively and qualitatively by trial products group. Triplicate values will be issued for each measurement and the average of the 3 replicates will be used for statistics analyses. Qualitative analyses will be done via comparison of ECG data to their normal ranges. Quantitative analyses will be done by tabulating raw data and change from baseline. Listings of 12-lead safety ECG with interpretation, morphology analysis and flag for clinically significant will be provided.

Number of subjects experiencing burning, pain, eruption, extravasation and inflammation at site injection will be tabulated per IMPs groups and overall. Pain at injection site will be measured using the Visual Assessment Scale (VAS) and VAS measurements for these subjects will be tabulated.

Physical examination will only be listed in CSR appendix 16.2.9.

#### **5.6.6. Concomitant medications and procedures**

Concomitant medications are those ongoing at or started after the first treatment application. Concomitant medications will be coded using the WHODRUG dictionary version September 2016. Concomitant procedures are therapies not coded as per WHODRUG dictionary.

Incidence of concomitant medications and procedures will be tabulated. The number and percent of subjects taking concomitant medications and concomitant procedures will be presented by trial product group. The denominator will be the number of subjects in the safety set.

Concomitant medications and procedures will be associated to trial product group according to the following rules:

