11.3.2 Data Sets Analyzed

There will be four subject sets defined for this trial: All enrolled subjects set, the Safety Set (SS), the Full Analysis Set (FAS) and the Per-Protocol Set (PPS).

All enrolled Subjects Set will include all subjects having signed their inform consent form. This set will be used for subject disposition summaries and individual listings.

The Safety Set will include all subjects, receiving at least one administration of IMP/AMP, regardless of the quantity. This set will be used for evaluation of safety and description of demographic data and baseline characteristics.

The Full Analysis Set will include all randomized subjects. This set will be used for evaluation of cardiac safety and description of demographic data and baseline characteristics.

The Per Protocol Set will be a subset of the FAS and will include all subjects who have no major protocol deviations throughout their whole trial period. Major deviations will be defined as having an impact on the primary criterion. Primary analysis will be performed on this set.

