### 3. STATISTICAL METHODS

#### 3.1. General considerations

After the database lock, the statistical analysis will be performed ██████████ under the supervision of GUERBET Biostatistician on the basis of the present document.

A quality control of the statistical analysis will be performed both by GUERBET and the CRO to ensure the reliability of the results.

The GUERBET validation strategy will be described in the Statistical Analysis Validation Plan which will be based on this present document.

Thorough description of all parameters reported will be presented separately by trial product or sequence group. Summary tabulated results will be provided by group and assessment time, if relevant or they will be replaced by the corresponding individual data listings if too few subjects are concerned.

Tabulations of quantitative parameters will include the following summary statistics: Number of Subjects, Mean, Standard Deviation, Minimum, Median and Maximum. If for a given parameter, the raw value has been collected with x decimal places, the mean, median and standard deviation will be rounded to x+1 decimal places, while the minimum and maximum values will be tabulated as reported with x decimal places.

Tabulations of frequencies for categorical data will include all possible categories and will display the number of observations in a category as well as the percentage (%) relative to the respective group. Percentages will be rounded to one decimal place. The category missing will be displayed only if there are actually missing values. Percentages will be calculated on the total of non-missing recorded categories.

All statistical tests will be performed at the significant threshold of 5% one sided.

SAS® Version 9.2 will be used for all descriptive summaries and ██████████ analyses.

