### 3.3. Determination of sample size

A total of 48 subjects will be included in the study trial.

The sample size is determined using published recommendations for a thorough QT trial [4].

$N$  can be estimated by 
$$N = 2 * [t_{\alpha}(\gamma) + t_{\beta'}(\gamma)]^2 [\sigma / (\delta - 10)]^2$$

where

- $\sigma^2$  is the within subject variability
- $\gamma = N - 2$
- $\beta' = 1 - (1 - \beta)1/L$  where  $\beta$  is the Type II error and  $L$  the number of measurements
- $\alpha$  is the Type I error
- $t_{\alpha}(\gamma)$  the critical values for a Student T distribution with  $\gamma$  degrees of freedom at an  $\alpha$  level.
- $\delta$  is the expected difference between active drug and placebo (0 if no difference expected, >0 if drug is expected to slightly increase QT).

Considering an expected intra-variability of the primary endpoint of  $\sigma = 9$  ms and an expected difference of  $\delta = 2$  ms between P03277 (two doses) and placebo, 40 subjects are needed to demonstrate non-inferiority with a non-inferiority margin of 10 ms, a power of  $1 - \beta = 85\%$  and a Type I error of  $\alpha = 5\%$  one-sided on the  $L = 9$  measurements.

This sample size is also sufficient to detect a difference of 5 ms (with an expected difference of 12 ms for at least one timepoint and an expected intra-variability of the primary endpoint of  $\sigma = 9$  ms) of the primary endpoint between moxifloxacin and placebo with a power of 85%.

To account for potential dropouts and/or unevaluable data points, 48 subjects will be randomized in the trial. The recruitment could be stopped before 48 subjects from the time the number of fully evaluable subjects for the primary criterion is 40. That is to say having took part to the study, until the last scheduled ECG holter recording.

A dropout is a subject who is prematurely discontinuing the trial before the end of the last holter ECG recording.

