### 5.2. Data sets analysed and protocol deviations

#### Data sets analysed

There will be four subject sets defined for this study: All enrolled subjects set, the Safety Set (SS), the Full Analysis Set (FAS) and the Per-Protocol Set (PPS).

All enrolled Subjects Set will include all subjects who signed their informed consent form. This set will be used for subject disposition summaries and individual listings.

All subjects who failed the screening visit (not selected) or withdrawn from the study before the randomization are screen-failed subjects and will be presented in the all enrolled data set. Those subjects have different data collected depending on the selection status i.e. complete screening visit and inclusion visit data collected for volunteers who have been selected at screening visit while only screening visit data were collected for subjects who did not comply with the eligibility criteria.

The Safety Set will include all subjects receiving at least one administration of IMP, regardless of the quantity. This set will be used for evaluation of safety and description of demographic data and baseline characteristics.

The Full Analysis Set will include all randomized subjects. This set will be used for evaluation of cardiac safety and description of demographic data and baseline characteristics.

The Per Protocol Set will be a subset of the FAS and will include all subjects who have no major protocol deviations throughout their whole trial period. Major deviations will be defined as having an impact on the primary criterion. Primary analysis will be performed on this set.

The number of subjects by analysis set will be tabulated by sequence group and overall.

The following table describes how the above defined subjects sets will be used in the different analyses conducted.

CONFIDENTIAL	STATISTICAL ANALYSIS PLAN N° GDX-44-006  VERSION N° 2.0      DATED: 24JUL2018  	  Page 17 / 57
--------------	--	---

Analyses Sets	Safety Set	Full Analysis Set (FAS)	Per protocol (PP) Set
Demographic data and baseline characteristics	✓	✓	✓ *
Exposure	✓		
Cardiac safety assessment		✓	✓
Safety assessment	✓		

\*: If the difference between FAS and PP set is greater than 10%

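### SAP 5.6.6 divides by-product concomitant-medication percentages by the whole Safety Set, so a Safety Set subject who withdraws before the fourth administration counts in the denominator of products never received.

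*SAP*

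**What the plan says.** SAP 5.6.6 sets the layout of the table: "The number and percent of subjects taking concomitant medications and concomitant procedures will be presented by trial product group". The next sentence sets the divisor: "The denominator will be the number of subjects in the safety set". The section also asks for ATC summaries by product and overall, and gives a grid that assigns each medication to one or more products according to the periods in which it started and ended.

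Three other places bear on this.

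- SAP 5.2 defines the set: "The Safety Set will include all subjects receiving at least one administration of IMP, regardless of the quantity". It does not require exposure to every product. The size of the set is not reported by product either: "The number of subjects by analysis set will be tabulated by sequence group and overall".
- SAP 3.1 gives the general rule for categorical tables, which "will display the number of observations in a category as well as the percentage (%) relative to the respective group".
- SAP 5.1 counts the subjects exposed to each trial product, as part of disposition.

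The protocol (11.3.2) defines the set slightly differently: "The Safety Set will include all subjects, receiving at least one administration of IMP/AMP, regardless of the quantity". Moxifloxacin is the auxiliary product (AMP). A subject who received only moxifloxacin is therefore inside the protocol's Safety Set and outside the SAP's.

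**The concern.** In a parallel-group trial, dividing by the Safety Set within each arm is routine. In a crossover the columns are products, and one subject belongs to up to four of them. Someone who leaves after two periods has no time at risk on the other two products, yet under 5.6.6 still counts in the divisor for both.

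The plan foresees withdrawal between periods. SAP 3.3 says "To account for potential dropouts and/or unevaluable data points, 48 subjects will be randomized in the trial", with 40 needed. Protocol 10.2 has subject stopping rules that prevent later administrations, and protocol 8.1.3.1 has biochemistry reviewed against those rules before each later dose.

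What is at stake is the comparison of medication use between products. Protocol 6.1.2 allows medication given to treat adverse events, so the table carries some safety information. If withdrawals fall unevenly across sequences, part of any contrast between columns reflects who withdrew.

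**Working it through.** The documents state no figure for this table, so there is nothing to reproduce. The check is direct arithmetic on the rule.

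**Inputs.** N = 48 randomised and 40 needed (SAP 3.3), an allowance of 48 − 40 = 8. The sequences are the examples in protocol 3.1: P/CD/PC/SD, CD/SD/P/PC, SD/PC/CD/P and PC/P/SD/CD. The number of users k and the withdrawal patterns are assumptions, because the documents give neither.

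**Formula.** Reported percentage = k/N. Exposure-based percentage = k/n, where n is the number of Safety Set subjects who received the product. Their ratio is n/N. All rows take a Safety Set of 48 and k = 10.

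| Subjects missing the product | n | n/N | Reported 10/48 | Exposure-based 10/n |
|---|---|---|---|---|
| 0 | 48 | 1.000 | 20.8% | 20.8% |
| 1 | 47 | 0.979 | 20.8% | 21.3% |
| 4 | 44 | 0.917 | 20.8% | 22.7% |
| 8 | 40 | 0.833 | 20.8% | 25.0% |

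**Pattern of withdrawal.**

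- *Two subjects per sequence stop after Period 2.* Each product is missed in two sequences, so 2 × 2 = 4 subjects miss it. The ratio is 44/48 = 0.917 in every column, and the columns stay comparable.
- *Two per sequence stop after Period 1.* Two subjects have then received only moxifloxacin and fall outside the SAP's Safety Set, so N = 48 − 2 = 46. Each of the three investigational products has 48 − 6 = 42 exposed: 42/46 = 0.913. Moxifloxacin has 42 exposed, of whom 40 are in the Safety Set: 40/46 = 0.870.
- *Eight subjects in P/CD/PC/SD stop after Period 2.* Placebo keeps 48 exposed and the 0.3 mmol/kg dose has 40. If 25% of those exposed use a medication, placebo shows 12/48 = 25.0% and the high dose 10/48 = 20.8%.

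**Numerators.** The grid in 5.6.6 assigns a medication present before dosing and still ongoing at study end to products 1 to 4, with no exception for a subject who left early. A medication started between the second and third administrations goes to product 1 as well as product 2, and one started after the fourth goes to none. Suppose 4 subjects miss a product and 10 of the 44 exposed are users, so the correct figure is 22.7%. If one of the 4 has an ongoing medication that the grid assigns to that product, the table shows 11/48 = 22.9%, which is slightly too high. Correcting the denominator alone would give 11/44 = 25.0%, which is further off.

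**The case against.** The best defence is that the denominator sentence only names the analysis set, Safety Set rather than Full Analysis Set, and that SAP 3.1 supplies the group-specific divisor. The table shells that could show column sizes are not visible in the public copy. This reading is possible, but it is not what the sentence says, and nothing in 5.6.6 limits the divisor to exposed subjects. At the least, a specific sentence and a general rule disagree, and a programmer would normally follow the specific one.

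Other objections stand, because they rule out stronger readings that a reader might infer.

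- *That any withdrawal causes the error.* SAP 3.3 counts as a dropout anyone who leaves before the end of the last Holter recording. That includes subjects already dosed with all four products, for whom the denominator is right.
- *That everyone who stops after Period 1 enters all four denominators.* Under the SAP's definition, a subject given moxifloxacin first who then stops enters none.
- *That the percentages are always too low.* This is true only for a fixed numerator. The attribution grid can outweigh the denominator effect.
- *That a 17% relative understatement is to be expected.* It needs all 8 subjects to miss the same product. The allowance also covers data that cannot be evaluated, and recruitment may stop before 48.

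It is also fair that counts stand beside the percentages, that exposure per product is tabulated under SAP 5.1, and that all concomitant medications are listed. A careful reader could approximate the right figure.

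**Conclusion.** The point holds, and it is minor. As written, SAP 5.6.6 puts Safety Set subjects who withdrew before the fourth administration into the denominator of products they never received, which conflicts with SAP 3.1. With the numerator fixed and a Safety Set of 48, the understatement runs from none, through 2.1% relative for one subject (1 − 47/48) and 8.3% for four (1 − 44/48), to 16.7% for eight (1 − 40/48). The last is an upper bound under the plan's own allowance. With balanced withdrawals after Period 2 the factor is the same in every column; distortion between products needs an uneven pattern.

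The direction of the net error in any one cell cannot be stated in advance, because the attribution grid also affects numerators. No hypothesis test or decision rule uses this table, and the QTcF analysis is untouched.

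**What to change.** In SAP 5.6.6, replace the denominator sentence with three rules:

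1. The denominator of each product column is the number of Safety Set subjects who received that product.
2. A subject counts in a product's numerator only if that product was received, whatever the attribution grid would otherwise assign.
3. The whole Safety Set is the denominator for the overall column only.

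Rules 1 and 2 belong together: changing the denominator alone could leave a withdrawn subject in the numerator of a column whose denominator excludes that subject.

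The moxifloxacin column also depends on which Safety Set definition applies, so the SAP and protocol definitions should be reconciled at the same time.

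The cost is a few lines of SAP text and a filter in the table program. No new data are needed. The SAP 5.1 exposure counts are a useful cross-check, but disposition is based on all consented subjects, so the column sizes should be taken from the dosing records within the Safety Set. If every Safety Set subject receives all four products, the table is unchanged.

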**End Period**

CONFIDENTIAL	STATISTICAL ANALYSIS PLAN N° GDX-44-006  VERSION N° 2.0      DATED: 24JUL2018	██████████  Page 38 / 57
--------------	---	--------------------------------

Start Period	1	2	3	4	5	6
1=Before first administration	-	trial product group 1	trial product groups 1, 2	trial product groups 1, 2, 3	trial product groups 1, 2, 3, 4	trial product groups 1, 2, 3, 4
2=Between first and second administration		trial product group 1	trial product groups 1, 2	trial product groups 1, 2, 3	trial product groups 1, 2, 3, 4	trial product groups 1, 2, 3, 4
3=Between second and third administration			trial product groups 1, 2	trial product groups 1, 2, 3	trial product groups 1, 2, 3, 4	trial product groups 1, 2, 3, 4
4=Between third and fourth administration				trial product groups 1, 2, 3	trial product groups 1, 2, 3, 4	trial product groups 1, 2, 3, 4
5=After fourth administration					-	-
6=Ongoing at the end of the study						-

Summary tables (number and % of subjects) grouped by the first and the fourth level of ATC code will be presented by trial product group and overall for concomitant medications.

[figure not shown]
Listing of all concomitant medications will be presented in CSR appendix 16.2.4.

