6.1.2 Prohibited Concomitant Treatments

Use of any prescription drugs (except for contraceptive pills, paracetamol and AE countermedication), herbal supplements medication, dietary supplements, and/or over the-counter (OTC) within 3 weeks prior to inclusion until the end of the confinement period will be prohibited.

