#### 2.3.1.6 *Concomitant medications*

Concomitant medications will be recorded at the time of informed consent form signature until end of the study.

CONFIDENTIAL	STATISTICAL ANALYSIS PLAN N° GDX-44-006 VERSION N° 2.0      DATED: 24JUL2018	██████████ Page 11 / 57
--------------	---	----------------------------

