### 5.6.2. Adverse events

All analyses of AEs will be based on the number of subjects with AEs (and not on the number of AEs) except otherwise specified and using the safety set.

Adverse events (AEs) will be coded using MedDRA version 21.0.

The time period for the assessment of AEs will be divided into 5 mutually exclusive and exhaustive periods:

- Before IMP/AMP: between informed consent signature and start of the first administration
- Period 1: between start of the first administration and start of the second administration
- Period 2: between start of the second administration and start of the third administration
- Period 3: between start of the third administration and start of the fourth administration
- Period 4: between start of the fourth administration and Day 12 included (date of Day 12 corresponds to date of Day 10 + 2 days not taking into account the time)
- After confinement period: during follow-up periods (> Day 12).

Events will be classified by trial products according to time of onset in the corresponding cycle related to trial products.

Events will be classified as treatment-emergent if they have started since the first administration.

Partial start dates/times will be queried. If information is not available to reliably allocate to a session and period, the allocation will be agreed at the data review meeting before database lock. If there is any doubt about treatment emergence, AEs will be classified as treatment emergent.

CONFIDENTIAL	
STATISTICAL ANALYSIS PLAN N° GDX-44-006
 
VERSION N° 2.0      DATED: 24JUL2018
 
██████████
	
██████████
 
Page 34 / 57

--------------	--	---

The number (%) of subjects having at least one AE as follows will be summarized for each trial product and overall for:

- At least one TEAE
- At least one AE with each of the following classification of intensity
  - Mild
  - Moderate
  - Severe
- At least one adverse reaction (relationship to trial treatment classified as ‘Related’)
- At least one AE with each of the following classifications of action taken with trial treatment:
  - Dose not changed
  - Trial product withdrawn
- At least one AE with each of the following classifications of outcome:
  - Recovered/resolved
  - Recovered/resolved with sequelae
  - Not recovered/Not resolved
  - Fatal

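### The SAP 5.6.6 attribution table charges concomitant medications to products whose window had already closed, and gives no product to those started after the fourth dose

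*SAP*

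**What the plan says.** SAP 5.6.6 defines the population of medications broadly: "Concomitant medications are those ongoing at or started after the first treatment application". It then sets the output: "The number and percent of subjects taking concomitant medications and concomitant procedures will be presented by trial product group". The denominator is the safety set. Further tables by first and fourth ATC level are given by product and overall.

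The link from medication to product is a grid of start window (rows) against end window (columns). Windows 1 to 6 are: before dose 1, dose 1 to 2, dose 2 to 3, dose 3 to 4, after dose 4, and ongoing at the end of the study. The grid reads:

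| Start window | End 1 | End 2 | End 3 | End 4 | End 5 | End 6 |
|---|---|---|---|---|---|---|
| 1 | none | 1 | 1,2 | 1,2,3 | 1,2,3,4 | 1,2,3,4 |
| 2 | | 1 | 1,2 | 1,2,3 | 1,2,3,4 | 1,2,3,4 |
| 3, "3=Between second and third administration" | | | 1,2 | 1,2,3 | 1,2,3,4 | 1,2,3,4 |
| 4 | | | | 1,2,3 | 1,2,3,4 | 1,2,3,4 |
| 5, "5=After fourth administration" | | | | | none | none |
| 6 | | | | | | none |

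Entries are the products charged, numbered in order of administration; none stands for the dash in the SAP.

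For adverse events, SAP 5.6.2 attributes by time of onset. It has a "Period 4: between start of the fourth administration and Day 12 included" and a separate category, "After confinement period: during follow-up periods".

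**The concern.** In rows 1 to 4 the products charged depend only on when the medication ended. A drug started and stopped between doses 3 and 4 is charged to products 1, 2 and 3. The right product is credited, but with two others whose windows had closed before the drug was started.

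Row 5 fails in the opposite direction. A drug started after dose 4 counts as concomitant under the definition in the same section, yet it carries the same dash as a drug that ended before dose 1. By analogy with a start after dose 1, which goes to product 1, it should go to product 4. As written, the fourth product in every sequence is credited with no new starts. A drug given for a Period 4 adverse event would have its event reported under product 4 and its treatment under no product.

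The by-product percentages are therefore wrong whenever such a start occurs. New starts are foreseeable: Protocol 6.1.2 allows paracetamol and medication for adverse events during confinement, and the latter is where attribution to a product is most informative.

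**Working it through.** **Inputs.** The grid in SAP 5.6.6; the four example sequences in Protocol 3.1, Table 1 (P/CD/PC/SD, CD/SD/P/PC, SD/PC/CD/P, PC/P/SD/CD); 12 subjects per sequence. There is no figure in the plan to reproduce. Medication rates below are assumptions.

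**Step 1: which rule is the grid?** Let *s* be the start window and *e* the end window.

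- End-only rule: products 1 to min(*e*−1, 4). It matches all 18 filled cells in rows 1 to 4, and fails in rows 5 and 6, where the grid has dashes.
- Overlap rule: products max(*s*−1, 1) to min(*e*−1, 4). Rows 1 to 5 hold 6+5+4+3+2 = 20 cells, of which 9 differ: 4 in row 3, 3 in row 4, 2 in row 5. That is 4×1 + 3×2 = 10 surplus product entries and 2 missing ones.

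**Step 2: expected crediting over the four sequences.** Suppose each sequence has one course started after a given product. Entries are the number of sequences, out of 4, in which a product is credited. They are the same whichever product is chosen.

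| Course length | Grid: own / each other | Overlap: own / each other | Difference, grid vs overlap |
|---|---|---|---|
| Within one window | 3 / 1 | 4 / 0 | 0.50 vs 1.00 |
| Into the next window | 3 / 2 | 4 / 1 | 0.25 vs 0.75 |
| Ongoing at end of study | 3 / 3 | 4 / 2 | 0 vs 0.50 |

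If all 48 subjects took one short course after the same product, the correct counts are 48 and 0, 0, 0. The grid gives 36 and 12, 12, 12, and the 12 subjects who had that product fourth appear in no product column.

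**Step 3: subject-level percentages.** The SAP counts subjects, so overlapping credits must be merged. For independent one-window courses with probability *p_m* after dose *m*, the product in position *k* is credited with probability 1 − ∏(1 − *p_m*) over *m* = *k* to 3, and 0 when *k* = 4. Average over the four sequences.

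Assume 25% after 0.3 mmol/kg (SD) and 5% after each other product:

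- SD: positions 4, 2, 1, 3 give 0; 1 − 0.75×0.95 = 0.2875; 1 − 0.75×0.95² = 0.3231; 0.25. Mean 0.8606/4 = 21.5%.
- Placebo: positions 1, 3, 4, 2 give 1 − 0.95³ = 0.1426; 0.05; 0; 0.2875. Mean 0.4801/4 = 12.0%.

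| Assumed true, SD vs placebo | Shown | Shown difference ÷ true difference |
|---|---|---|
| 25% vs 5% | 21.5% vs 12.0% | 0.48 |
| 30% vs 10% | 27.6% vs 18.5% | 0.45 |
| 40% vs 20% | 38.4% vs 30.2% | 0.41 |

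With equal true rates of 10%, positions 1 to 4 give 0.271, 0.19, 0.10 and 0, so every product shows 0.561/4 = 14.0%.

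**The case against.** The strongest defence is that rows 1 to 4 follow one consistent rule: charge every product received by the time the medication ended. The SAP never adopts an overlap rule, so calling seven of the nine cells wrong imposes a standard from outside. That has some force for rows 3 and 4 taken alone, but the cumulative reading would charge a start after dose 4 to all four products, and row 5 charges it to none. The SAP gives no rationale for either part. The cumulative rule is also a poor basis for a table meant to separate products.

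The definition in 5.6.6 says what counts as concomitant, not which product it belongs to, and the adverse event rule does not govern medications. So the mismatch with those texts is an inconsistency between parts of the plan rather than a strict contradiction. It still leaves medications that qualify as concomitant without any product.

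The two row 5 cells are wrong only for starts up to Day 12; a start during follow-up should not be charged to product 4. The grid has no such cut.

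On size, the rates are assumed, Protocol 6.1.2 bans most medication during confinement, and SAP 3.1 lets listings replace summaries when few subjects are concerned. At 5% after SD and 0% elsewhere, the expected counts among 48 subjects are 1.8 against 0.6, where the truth is 2.4 against 0. The crossover balance also means no false difference between products is expected when true rates are equal. All of this limits the consequence but does not make the table right.

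**Conclusion.** The table is wrong as written. It adds products whose window had closed before the medication began, and it drops starts between dose 4 and Day 12 from every product column. Nine of 20 cells need changing, the two in row 5 only for starts up to Day 12.

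The effect is to alter the level of each percentage and pull products together: the expected count difference falls to one half of the true one for one-window courses, and to one third of the overlap value for courses running into the next window; it vanishes for courses ongoing at the end. These ratios rest on equally filled sequences; the percentages also rest on assumed rates and independent one-window courses.

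This is a minor point. Only descriptive by-product tables are affected. The primary QTcF analysis, assay sensitivity, the concentration-QTc model, Per Protocol membership, the adverse event tables and the listings do not depend on it. Medications started after dose 4 remain in the listing and in the overall column of the ATC tables, but the SAP promises no overall column for the general count of medications and procedures.

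**What to change.** Replace the grid in SAP 5.6.6 with a stated rule: attribute each medication or procedure to every product from its start window through its end window, with window 5 closing at Day 12 as in SAP 5.6.2. The cells become:

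- Rows 1 and 2: unchanged.
- Row 3 (ends 3, 4, 5, 6): 2; 2,3; 2,3,4; 2,3,4.
- Row 4 (ends 4, 5, 6): 3; 3,4; 3,4.
- Row 5: product 4 if started up to Day 12; otherwise a separate follow-up category.

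The Day 12 split is needed because recording is long, "Concomitant medications will be recorded at the time of informed consent form signature until end of the study", while under Protocol 6.1.2 non-exempt medication only "until the end of the confinement period will be prohibited". Without it, product 4 would be charged with unrelated drugs taken during follow-up.

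The cost is one replaced SAP table and one extra cut in the derivation, already defined for adverse events. No new data are required.
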